3.10.3 Exposure of P1101 Administration

Variable used for calculation:

Variable Name \ Description

EXSTDTC = min (EXDAT, Date and Time of P1101 Administration)

EXENDTC = max (EXDAT, Date and Time of P1101 Administration)

Treatment Exposure [days] = EXENDTC – EXSTDTC + 14,

Maximum Dose Level [ug]: sorting by unique subject id and use the proc sql to choose the maximum dose level in each subject,

Cumulated Dose [ug]: sum of all used dose by subject,

Mean Dose Level [ug/4 weeks]: 28 x Cumulated Dose [ug] / Treatment Exposure [days]

3.10.4 Interpretation of HADS scores

Total score of depression and anxiety is interpreted as follows:

- Score 0-7: Normal
- Score 8-10: Mild
- Score 11-14: Moderate
- Score 15-21: Severe

4 Statistical and Analytical Procedure

4.1 Analysis Populations

4.1.1 Enrolled Population

The enrolled population will include subjects who have signed an informed consent form.

4.1.2 Intent-to-Treat Population (ITT)

The ITT population will include all treated subjects.

4.1.3 Per Protocol Population (PPP)

The PPP will consist of subjects included in the ITT who are exposed to treatment and have all measurements needed for assessment of the primary endpoint for at least 1 post-baseline visit, and do not have a major protocol deviation.

4.1.4 Safety Population

The Safety Population will include all subjects who have received at least one dose of study drug. For this single arm study, ITT and safety populations are identical.

4.2 Protocol Deviation

The following are considered potential protocol deviations:

- No diagnosis of PV.
- Prior therapy does not match with protocol requirements in terms of types of previous therapy regimens.
- No baseline spleen size measurement in the protocol-specified time windows.
- Subjects who take <80% of the prescribed dose over the total duration of study drug dosing as calculated by the Sponsor based on the drug accountability documented by the site staff and monitored by the Sponsor/designee.

Other observations made during the study will also be considered. All potential protocol deviations will be reviewed prior to database lock. For every potential protocol deviation, a general decision will be made whether to regard it as major or minor, and approved by the Sponsor before database lock. The PPP will be used for efficacy sensitivity analysis.

4.3 Statistical Analysis

This section describes the data analysis in detail. The statistical methods are planned in accordance with the study protocol (Section 17) and in accordance with ICH E9 Statistical Principles for Clinical Trials.

4.3.1 General Principles

Statistical package SAS (version 9.4 or higher) will be used for analysis and for generation of tables, figures and listings (TFL).

In general, data will be presented under group “P1101” as well as overall and by time-point. All data included in the study database will be listed.

4.3.1.1 Descriptive statistics

For categorical data (e.g. response to treatment: responder) standard set of summary statistics will be counts and percentages. Missing, unknown, not available, not applicable or not done categories will be included; therefore, the percentages will be calculated of total number of patients in the set. This approach was selected because it is close to intent-to-treat principle.

For continuous data (e.g. level of lymphocytes) the following descriptive statistics will be presented: number of available observations, mean, standard deviation (SD), median, interquartile range (IQR: Q1-Q3), minimum, and maximum.

Confidence intervals will be present if appropriate.

For time-to-event data (e.g. Time to first peripheral blood count response) KM method will be used for estimating the distribution, median with 95% CI will be presented.

4.3.1.2 Patients' data listings

The following columns will be used for identification of the patients in each listing (whenever applicable):

- Patient ID and Week (Visit).
- For listings of abnormal values (e.g. abnormal values of laboratory assessments, vital signs) and for listing of adverse events the last administered dose (dose administered/prescribed at previous visit) before blood sampling, examination or start of AE will be presented in the listing.

Data listings will be sorted by 'Patient ID' and in chronological order of visits (including unscheduled visits).

4.3.1.3 Rounding procedures

The following rounding procedures will be used:

- Min, Max: same number of decimal places as original value
- Mean, Median and its confidence intervals, Q1, Q3: one more decimal place than original value
- SD: two more decimal places than original value
- Percentages:
 - Safety variables: one decimal place
 - Efficacy variables: two decimal places
 - In case that percentages are very close to 0 or 100: more decimal places can be used.

4.3.1.4 Unscheduled/ repeated assessments

Unscheduled or repeated assessments performed due to safety reasons will only be listed with an exception of assessments which are the last assessments before the first study drug product administration - those will be used as baselines.

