### 15.3.8 Ocular Examination

All subjects will have an ocular examination at screening and at the EoT visit. The examination will consist of visual acuity assessment, slit lamp examination, tonometry, and fundus examination. Clinically relevant ophthalmological disorder (due to diabetes mellitus or hypertension) at screening will be an exclusion criterion. In addition to scheduled examinations, an ophthalmologist consultation is mandatory for all subjects reporting worsening vision or visual symptoms. P1101 treatment will be discontinued in subjects who develop a new ophthalmologic disorder during the study.

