### 16.1 Adverse Events

An adverse event (AE) is any untoward medical occurrence in a subject or clinical trial subject administered a medicinal product and which does not necessarily have a causal relationship with this treatment. All AEs occurring during the course of the clinical trial (i.e., from signing the informed consent form onwards through the treatment phase until the safety follow-up visit) will be collected, documented, and reported by the Investigator. Details on AE collection will be available in the eCRF collection guideline.

All AEs, serious and non-serious, will be fully documented on the appropriate eCRFs. For each AE, the Investigator will provide the onset, end, intensity, treatment required, outcome, seriousness, and action taken with the study drug. The Investigator will determine the relationship of the investigational drug to all AEs and record it in the eCRF. When assessing whether an AE is causally related to the study drug, the Investigator should consult the IB and use his/her clinical judgement and the subject's underlying disease before rendering an assessment.

All collected AEs will be coded according to the Medical Dictionary for Regulatory Activities (MedDRA). AEs and laboratory parameters will be graded according to CTCAE Version 5.0, (<http://ctep.cancer.gov>).

Adverse event monitoring should be continued until the safety follow-up visit/EoS or until AE resolution/stabilization, whichever occurs first. Safety follow-up visit is 28 days after end of treatment visit. AEs will be regarded as treatment-emergent if the time of onset or worsening is after or on the first intake of study drug.

Disease progression of PV should not be regarded or reported as an AE unless it is associated with a separate AE. Relationship will be assessed with not related, unlikely related, possibly related, probably and definitely related. Action taken will be described as dose increased, dose not changed, dose reduced, drug interrupted, drug withdrawn, and unknown.

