### 16.2 Abnormal Clinical Laboratory Test Results

All clinically significant abnormal laboratory tests occurring during the study will be repeated at appropriate intervals until they return to baseline or to a level deemed acceptable by the Investigator and the Sponsor's clinical monitor (or his/her designated representative), or until the abnormality is explained by an appropriate diagnosis. Clinically significant abnormal laboratory tests that result in a change in study drug dosage, discontinuation of the drug, or require intervention or diagnostic evaluation to assess the risk to the subject, or are otherwise clinically relevant, should be recorded as AEs in the eCRF. Clinical diagnosis should be provided whenever possible. If no clinical diagnosis is available, the increase/decrease in the laboratory parameter may be recorded as an AE term. When an abnormal laboratory or test result corresponds to a sign/symptom of an already reported AE, it is not necessary to separately record the laboratory/test result as an additional event.

Laboratory abnormalities that do not meet the definition of an AE should not be reported as AEs. A Grade 3 or 4 event (severe), as per CTCAE, does not automatically indicate an SAE unless it meets the definition of serious as defined in the protocol and/or as per Investigator's discretion. A dose modification or medication for the laboratory abnormality may be required by the protocol in [Section 12.5.2](#) and should not contribute to the designation of a laboratory parameter abnormality as an SAE.

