3.2 Study Visits/ Time-Points

Number of week and number of study visit will be included in label of study visits. The labels will be as follows: Screening, Baseline, Week 2 (V2), Week 4 (V3), Week 6 (V4), ..., Week 52 (EOT), Premature discontinuation (for End-of-Study visit of premature discontinued patients), FU (for Safety Follow-Up visit). Unscheduled visit will be labeled as 'UNS' and presented in chronological order (UNSV.c), v is visit no. and c is the times of unscheduled visit between Visit v to Visit v+1. Unscheduled visit is visit recorded as '※' in EDC.

Assessment visits will be labeled as follows: Week 12 (V7), Week 24 (V13), Week 36 (V19), Week 52 (EOT). Time-window is defined as +/- 3 days of a scheduled visit date. Deviation from the time-window will usually not be adjusted, unless specified otherwise.

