4.3.6.2 Physical Examination

Results of physical examination by visit will be reported in frequency tables.

4.3.6.3 Vital signs, ECG parameters, Safety Laboratory data Lung X-Ray, Heart ECHO, and Ocular examination

Values out of normal ranges will be flagged in data listings. Laboratory values will be presented in conventional units. No formal statistical tests comparing results of vital signs and safety laboratory data will be performed.

Absolute values and changes from baseline will be descriptively analyzed by study visits. Count (and percentage) of values in the normal ranges, abnormal clinically significant and not clinically significant will be displayed in summary tables together with descriptive statistics.

In tables and listings all local and central assessment will be presented (and clearly distinguished). In figures local and central assessment will be presented separately.

For assessments without numeric result (e.g. result positive/negative, normal/abnormal) counts and percentages by visit will be presented in the tables and shift tables will be used for presentation of change between Screening and EOT visit/ V27.

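### Post-baseline safety results obtained off schedule go only to listings, no table gives the worst post-baseline CTCAE grade, and the shift-table endpoint for early stoppers is ambiguous

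*SAP*

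**What the plan says.** **Off-schedule results.** SAP 4.3.1.4 states: "Unscheduled or repeated assessments performed due to safety reasons will only be listed". The one exception is the last assessment before first dose, which serves as baseline, in line with SAP 3.4.

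**Tables.** For numeric safety data SAP 4.3.6.3 states: "Absolute values and changes from baseline will be descriptively analyzed by study visits". It adds counts of normal, clinically significant abnormal and not clinically significant abnormal values. Non-numeric results get counts and percentages at each visit, and in addition "shift tables will be used for presentation of change between Screening and EOT visit/ V27".

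**Protocol.** Section 16.1 says "AEs and laboratory parameters will be graded according to CTCAE Version 5.0", and section 16.2 says "All clinically significant abnormal laboratory tests occurring during the study will be repeated at appropriate intervals". Section 15.3.8 schedules eye examinations at screening and end of treatment, requires a specialist consultation for any subject who reports visual symptoms, and adds: "P1101 treatment will be discontinued in subjects who develop a new ophthalmologic disorder during the study".

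**Early stoppers.** SAP 3.2 lists Week 52 (EOT) and, as a separate label, "Premature discontinuation (for End-of-Study visit of premature discontinued patients". SAP 3.6 defines EOT as the final visit of a treatment period that may end in premature discontinuation. Protocol 8.1 holds the EoT visit when a subject discontinues. Appendix 1 puts Month 12 and premature discontinuation in one End of Treatment column.

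**The concern.** A safety table should let the reader see how bad each measure became in each patient. Results taken between visits, or added because something looked wrong, are among those most likely to hold a peak, and here they can be found only by reading listings. The protocol promises CTCAE grading of laboratory parameters, but the SAP specifies no table that uses the grades.

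This is an open-label, single-arm study, and whether a laboratory value becomes an adverse event depends on the investigator's assessment. A graded laboratory table is the objective check on that assessment.

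The second issue is how the SAP will be programmed. The visit labels in SAP 3.2 and the definition in SAP 3.6 lead to different shift tables for patients who stop early.

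**Working it through.** The plan states no figure on this point, so there is none to reproduce. The check is a visit count and a comparison of sections.

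**1. Visits.** Dosing visits run from Week 0 to Week 52 every 2 weeks.
- Number of visits: 52/2 + 1 = 27. Post-baseline visits: 27 − 1 = 26.
- Visit number = week/2 + 1, so Weeks 12, 24, 36 and 52 are V7, V13, V19 and V27. These match the labels in SAP 3.2.

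**2. Which tests are exposed (Protocol Appendix 1).**
- Hematocrit, platelets, WBC, ALT, AST, GGT and bilirubin are in the small panels, taken at every visit. Only values between visits are lost from their tables.
- The WBC differential, including neutrophils, is in the large hematology panel, scheduled post-baseline at Weeks 12, 24, 36 and 52. That is 4 of 26 visits, leaving 26 − 4 = 22 without a scheduled count. Creatinine, amylase, lipase and TSH are in the large chemistry panel on the same schedule.
- Protocol 12.5.2 uses neutrophil thresholds for dose modification, so counts may well be drawn at some of those 22 visits.
- The only scheduled post-baseline eye examination is at end of treatment. A symptom-triggered consultation is unscheduled by nature.

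**3. Where those results go.** Under SAP 4.3.1.4 they are listed. SAP 4.3.1.1 reports minimum and maximum at each visit, but these cannot recover a value left out of that visit. SAP 4.3.6.3 also says that all local and central assessments appear in tables as well as listings. The likely meaning is that both laboratories are shown, but the sentence is not reconciled with the listing-only rule.

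**4. Direction of the effect.** For a subject with scheduled results S and off-schedule results U, max(S ∪ U) ≥ max(S). The number of subjects whose worst grade reaches a given level can therefore only stay the same or rise when U is included. By-visit tables do not give that number even for scheduled data: one abnormal subject at Week 12 and one at Week 24 look the same whether they are one person or two.

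**5. What the adverse event tables recover.** SAP 4.3.6.1 reports TEAEs by maximum CTCAE grade whatever the visit. Under Protocol 16.2 a laboratory result is recorded as an event if it is clinically significant and it changes dosing, needs intervention or diagnostic work-up, or is otherwise clinically relevant. Other abnormalities, whatever their numerical grade, stay outside those tables.

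**6. The shift endpoint.**

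| Source | Discontinuation visit treated as |
|---|---|
| SAP 3.2 | separate label, not Week 52 (EOT) |
| SAP 3.6 | EOT, as the final treatment-period visit |
| Protocol 8.1 | the EoT visit |
| Protocol Appendix 1 | same column as Month 12 |
| SAP 4.3.6.3 | EOT visit/V27, not resolved |

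A programmer working from the SAP 3.2 labels would leave early stoppers out of the shift. One working from SAP 3.6 would include them. The shift also starts at Screening, whereas SAP 3.4 defines baseline as the last value before dosing.

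**The case against.** **The adverse event tables already show peak toxicity.** They cover first dose to 30 days after the last dose, are not tied to scheduled visits, report maximum grade, and include separate tables for serious events and events leading to discontinuation. Protocol 12.5.2 requires interruption for Grade 3 or 4 toxicity, so a severe and clinically significant laboratory result should also reach the adverse event form. This stands for the most serious findings. It does not cover abnormalities that the investigator does not record.

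**Repeat tests often document recovery.** Protocol 16.2 continues repeats until the value returns to baseline or an acceptable level. This is also true, so the direction shown above applies to the incidence of peak abnormalities and not to every summary, such as by-visit means.

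**Nothing is hidden.** All data are listed and abnormal values are flagged. In a study of 30 patients the listings can be read. That lowers the stakes, but listings do not yield a rate.

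**Stronger readings.** A reader might infer that off-schedule results are kept out of every summary table. They are not: the adverse event tables are unaffected, and pre-dose unscheduled values serve as baseline. A reader might also infer that patients who stop early disappear from the safety tables. The documents do not support this. Such patients are in the Safety Population, in the by-visit tables up to their last visit, and in the adverse event and discontinuation tables. A patient withdrawn for a new eye disorder is due an EoT eye examination, which enters the shift table on the SAP 3.6 reading.

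**Conclusion.** The concern holds in a limited form. Followed as written, the SAP can understate peak abnormalities in the laboratory, ECG, vital-sign and examination tables, and it specifies no table for the laboratory grades that the protocol promises. The exposure is small for tests taken every 2 weeks and larger for neutrophils, the other large-panel tests and symptom-triggered eye examinations. For early stoppers there is an unresolved ambiguity in the shift tables, not a demonstrated loss.

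The number of patients affected cannot be derived. The 37 non-completers among 254 in the randomized phase 3 study summarised in Protocol 5.3 (254 − 217) pool both treatment arms, and non-completion does not mean that no EoT result exists. They do not size the gap here.

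The conclusion rests on two assumptions. A large-panel test drawn at a visit where it is not scheduled is taken to be an unscheduled assessment under SAP 4.3.1.4. The flowchart columns are taken to be as they read in the text, which should be confirmed against the original PDF. The point about the missing worst-grade table depends on neither.

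**What to change.** 1. **SAP 4.3.1.4 and 4.3.6.3.** Keep the by-visit tables on scheduled values. State that the listing-only rule governs those tables, and reconcile it with the sentence on local and central assessments.
2. **New tables.** Add shifts from baseline, as defined in SAP 3.4, to the worst post-baseline CTCAE v5.0 grade for laboratory parameters, and to the worst category for ECG, ocular examination and HADS. Use all results after first dose through safety follow-up, including unscheduled, repeat and premature-discontinuation results. The HADS boundaries must be aligned first: Protocol 15.3.1.5 has moderate as 11–15 and SAP 3.10.4 has 11–14.
3. **Shift endpoint.** Replace the Screening to EOT visit/V27 wording with baseline to V27 or the premature discontinuation visit, and align SAP 3.2 with SAP 3.6.
4. **Missing assessments.** Show subjects with no post-baseline assessment as missing and do not carry the screening value forward. Under Protocol 15.3.9 early stoppers have no end-of-treatment lung X-ray unless safety follow-up needs one, and a carried-forward screening film would read as no change.

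The cost is SAP wording and a few extra tables, with no new data and no change to patient care. Abnormality rates may look slightly less favourable.

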4.3.1.5 Missing data and handling of prematurely discontinued patients

Missing data includes missing assessments as well as data missing due to premature termination. No imputation methods are planned to be applied to study data.

4.3.1.6 Methods for handling of incomplete dates/ times

Dates of Adverse Events

For calculation of adverse events duration and for summaries of adverse events by 3 months periods incomplete date and times will be imputed as follows:

Protocol P1101 in Japanese PV (A19-201)

Dates of Onset: If AE is recorded at the same month and year when the study drug product was firstly administered to patient then onset date of AEs will be imputed by date of the first administration; otherwise onset date of AEs will be imputed by date of the first day in corresponding month or year.

Dates of End: End dates of AE will be imputed by date of the last day in corresponding month or year.

Dates of Concomitant Medications, adverse events and changes in dosing have to be cleaned before DB lock for final analysis. Hence the questionable cases will be solved individually if needed. The solution will be documented in data review meeting minutes.

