3.8 Adverse events

Adverse event (AE) is defined as any event recorded on "Adverse Event" page of e-CRF. Events occurred before date when the informed consent has been signed have to be recorded in "Medical History" page of e-CRF.

Serious adverse event (SAE) is any AE that is reported as serious, as indicated on the "Adverse Event" page of e-CRF.

Treatment-emergent adverse event (TEAE) / treatment emergent SAE (TESAE) is any AE / SAE occurred since date of the first study drug product administration (including that time). If onset date of AE is not complete and beginning of AE after the first drug administration cannot be excluded the AE is considered as treatment emergent. An AE, having been absent pretreatment, or worsens relative to the pretreatment state is also considered as treatment emergent. All questionable cases have to be clarified and approved before analysis.

AE leading to permanent treatment discontinuation, AE leading to dose increasing/ decreasing/ interruption and AE of special interest (AESI) are AEs as indicated on the "Adverse Event" page of e-CRF.

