3.10 Derivation and Algorithms

3.10.1 Duration of AEs

Variable used for calculation:

Variable Name \ Description

AESTDAT Start date

AEENDAT End date

Duration of AEs (number of days) will be calculated from date of AE onset and AE end using

AE_DiffDays=AEENDAT - AESTDAT;

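### An adverse event dated only by year, in the year of first dose, is imputed to 1 January: it stays treatment-emergent but carries a pre-dose date in the by-period table

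*SAP*

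**What the plan says.** SAP 4.3.1.6 gives the rules for incomplete adverse event dates and limits their use: "For calculation of adverse events duration and for summaries of adverse events by 3 months periods". If the event falls in the month and year of first dose, "onset date of AEs will be imputed by date of the first administration". Every other partial onset goes to the start of whatever period is known: "otherwise onset date of AEs will be imputed by date of the first day in corresponding month or year". For the other end of the event, "End dates of AE will be imputed by date of the last day in corresponding month or year". The same section requires adverse event dates to be cleaned before database lock. Questionable cases are then settled individually and documented.

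Treatment-emergent status is handled separately in SAP 3.8. When the onset date is incomplete and "beginning of AE after the first drug administration cannot be excluded the AE is considered as treatment emergent".

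SAP 3.10.1 defines duration in whole days as "AE_DiffDays=AEENDAT - AESTDAT". SAP 3.7 numbers study days inclusively, adding 1 from first dose onward. SAP 4.3.6.1 lists a general overview of treatment-emergent events by 3-month periods. It lists no summary table of event duration.

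**The concern.** The imputation rule and the treatment-emergent rule treat the same uncertainty differently. SAP 3.8 resolves an ambiguous onset in favour of treatment-emergent. SAP 4.3.1.6 does so only when the month is known. When only the year is known, and it is the year of first dose, the imputed date contradicts the classification.

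Two outputs use the imputed date. In the by-period overview, the event is counted as treatment-emergent but is dated before the first on-treatment period, and the SAP does not say where it then goes. In the derived duration, time before treatment is added to an event that the SAP treats as having begun on treatment.

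The duration formula raises a smaller question of consistency: an event that starts and stops on one day gets a duration of zero.

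**Working it through.** The documents state no figure on this point, so there is none to reproduce. The check applies the SAP rules as written. The dates are illustrative assumptions; 2020 lies inside the planned study period in the Protocol synopsis (September 2019 to August 2021).

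**Onset rule**

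- Month and year known and equal to those of first dose: onset = first-dose date.
- Otherwise: onset = first day of the known month, or 1 January if only the year is known. There is no floor at first dose.

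**Where the rule fails.** The rules were applied to every first-dose date in 2020 and every true onset from 0 to 392 days after first dose (366 × 393 = 143,838 combinations).

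| Known part of onset | Combinations | Imputed before first dose |
|---|---|---|
| Month and year | 143,838 | 0 |
| Year only, year of first dose | 67,161 | 66,795 (99.5%) |
| Year only, later year | 76,677 | 0 |

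The 67,161 − 66,795 = 366 exceptions are the first doses on 1 January. These are counts over a date grid and say nothing about how often such dates will occur. They show that the failure is confined to one cell and is near-total within it.

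**Size of the displacement.** For an onset recorded only as 2020, the imputed study day under SAP 3.7 depends on the first dose:

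| First dose | Imputed study day |
|---|---|
| 15 January 2020 | −14 |
| 2 March 2020 | −61 |
| 15 June 2020 | −166 |
| 1 December 2020 | −335 |

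For 15 June, the days from 1 January are 31 + 29 + 31 + 30 + 31 + 14 = 166. The screening period in Protocol 8 is 28 days, and SAP 3.8 sends events before consent to medical history. In the last three rows the imputed date is therefore earlier than an adverse event could have been recorded, if screening keeps to its window.

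**Effect on duration.** First dose 15 June 2020, onset recorded as 2020, end 20 July 2020:

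- SAP formula with the imputed onset: 1 January to 20 July = 201 days.
- Same formula with onset at first dose: 15 June to 20 July = 35 days (36 counted inclusively).
- Excess: 201 − 35 = 166 days. If the event did begin on treatment, 35 elapsed days is the longest it can have lasted.

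**Duration convention.** With complete dates, an event starting and stopping on 1 July gets 0 days, and one from 1 to 3 July gets 2. Inclusive counts are 1 and 3. The difference is always one day.

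**The case against.** The strongest reply is that this is a fallback rule for a case that should hardly arise. Visits are every 2 weeks, so a missing month should be unusual. SAP 4.3.1.6 requires cleaning before lock and individual resolution of questionable cases, and SAP 3.8 also requires questionable cases to be clarified before analysis. This stands as an argument about frequency. It does not rescue the rule, which exists for dates that survive cleaning and explicitly provides for year-only dates. Double programming under SAP 4.3.1.7 would not detect the problem either, because both programs would follow the same specification.

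A reader might infer that the main safety tables are wrong, since SAP 4.3.6.1 also describes treatment-emergent events by date relative to first dose. The documents do not support that. The imputation is limited to duration and the 3-month summaries, and SAP 3.8 has its own rule for incomplete onsets. The tables by system organ class, preferred term, severity, relationship and seriousness need not change. Nor can one say that the event drops out of every period, because the SAP does not specify the assignment.

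A reader might also call the missing +1 an error that makes duration summaries wrong. End minus start is a recognised elapsed-days measure, Protocol 15.3.11 collects start and stop times, and no duration summary table is listed. The documents also do not say whether the end date is the last day with symptoms or the day of resolution. It is tempting to add that expected reactions such as flu-like symptoms are the short events most affected, but the documents give no durations for them. What remains is a zero for same-day events and an unstated convention.

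**Conclusion.** The point holds in a narrow form and is minor. For an onset known only by year, in the calendar year of first dose, SAP 4.3.1.6 produces a date before treatment unless first dose was on 1 January, while SAP 3.8 calls the same event treatment-emergent. One listed output is exposed, the overview by 3-month periods, together with any derived duration. The displacement equals the time from 1 January to first dose, 166 days in the June example. How many such dates will remain at lock is not known from the documents and should be small.

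The duration formula is a matter of consistency and labelling. The primary endpoint and the sample size are not touched.

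**What to change.** **SAP 4.3.1.6.** Replace the onset rule with this: when the known part of the onset date does not exclude onset on or after first dose, and the event did not end before first dose, impute onset as the later of the first-dose date and the first day of the known month or year. Otherwise use the first day of the known month or year.

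The end-date condition is needed because Protocol 16.1 collects adverse events from consent. With onset June 2020, end 10 June and first dose 15 June, the present first branch already gives 10 − 15 = −5 days, and an unconditional floor would extend that fault to year-only dates.

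**SAP 3.10.1.** Either add 1 to the `AE_DiffDays` formula, which matches the inclusive count in SAP 3.7, or keep the formula and label the result as elapsed days.

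The cost is a few SAP lines before programming, with no new data and no change in trial conduct.
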